### 11.1 Sample Size Determination

Thirty-eight subjects per group will provide 90% power for the comparison of ifetroban and placebo with respect to the change from baseline in SNOT-22 scores at Week 8 (two-sided, level 0.05), assuming a common standard deviation of 16 and a true difference is 12.

### 11.2 Subject Populations for Analysis

## 11.2.1 Safety Population

All subjects who received at least one dose of study medication will be included in the Safety Population.

Treatment emergent period for Safety Population is defined as the time from the first administration of study medication to the end of the post-treatment Period.

# 11.2.2 Intent-to-Treat Population

The Intent-To-Treat (ITT) Population will consist of all treated subjects with at least one post-baseline assessment of SNOT-22.

# 11.2.3 Per Protocol Population

The Per Protocol (PP) Population will consist of all subjects in the ITT population with no major protocol violations, including violation of inclusion or exclusion criteria or insufficient dosing. Inclusion of subjects in the PP Population will be determined prior to unblinding.

# 11.3 Subgroup analysis

To assess the consistency of treatment effects across the subgroup levels, and to examine baseline biomarkers for their potential value to predict treatment response, exploratory subgroup analyses will be conducted for the change from baseline in SNOT-22 with respect to age group, gender,

region, race, baseline SNOT-22, baseline TNSS, baseline ACQ-7 and selected biomarkers prior to the study. The details will be provided in the Statistical Analysis Plan.

#### 11.4 Randomization

Subjects will be randomized using a 1:1 randomization ratio for ifetroban 200 mg daily for eight weeks, or placebo daily for eight weeks.

### 11.5 Methods for Handling Missing Data

All missing data will be queried. Missing efficacy data which are not retrievable through queries will be imputed. Binary response variables will be imputed by treating the missing data as a non-response, i.e., non-responder imputation. Missing data for continuous variables will be imputed using Last Observation Carried Forward. Sensitivity analyses may be performed to assess the impact of the imputation technique(s).

### 11.6 Data Analysis Plan

### 11.6.1 Demographic and Baseline Parameters

Demographic and baseline characteristics will be summarized using descriptive statistics or frequency tables, by treatment group and overall.

# 11.6.2 Exposure and Compliance

Exposure and compliance will be summarized for the Safety Population by treatment group and overall. Comments recorded on the Study Drug Accountability CRF page will not be applied in the computation of compliance.

Exposure is the duration (days) of treatment, computed as:

Exposure = Date of Final Dose- Date of Baseline Visit + 1.

Treatment compliance will be calculated as:

Compliance (%) = 100\*(Total Number of Capsules Dispensed-Total Number of Capsules Returned)/(4\*Exposure).

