#### PLACEBO OR IFETROBAN CAPSULES 50MG

Quantity: 75 Capsules

Instruction: Take capsules by mouth as directed.

Store at controlled room temperature,  $20^{\circ}\text{C} - 25^{\circ}\text{C}$  ( $68^{\circ}\text{F} - 77^{\circ}\text{F}$ )

Caution: New Drug-Limited by Federal law to investigational use

Cumberland Pharmaceuticals Inc.

Additionally, each individual bottle will be labelled with a unique numeric code that identifies the contents to the unblinded sponsor representative. Four (4) capsules each of IMP (oral ifetroban or matching placebo) will be taken by mouth per daily dose during the Treatment Period.

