#### **Week 4 Treatment Visit**

After four weeks of treatment, subjects will return to the site for Week 4 Treatment Visit.

- Record all medication use with start date and dose and check for prohibited medications.
- Inquire about AEs/Serious Adverse Events (SAEs) and IMP tolerability
- Perform a limited physical exam with vital signs (blood pressure, heart rate, respiration rate, body temperature, weight)
- Administer TNSS, ACQ-7, and SNOT-22
- Obtain spirometry, PNIFR and FeNO
- Perform serum/urine pregnancy test (for women of childbearing potential) Confirm subject is protected by one of the following acceptable forms of effective contraception during the study:
  - Established use of oral, injected or implanted hormonal contraceptive
  - "Double barrier" methods (i.e., Double Intrauterine device with copper or intrauterine system with progestogen and barrier contraceptive [condom, diaphragm or cervical/vault caps] used with spermicide [foam, gel, film, cream or suppository])

- Female sterilization (e.g., tubal occlusion, hysterectomy or bilateral salpingectomy)
- Male sterilization with post-vasectomy documentation of the absence of sperm in the ejaculate; for female subjects enrolled in the study, the vasectomized male partner should be the sole partner for that subject
- Collect urine and blood samples for eicosanoid metabolites.
- Collect nasoabsorptive matrix for eicosanoid measurements.
- Conduct a smell test (UPSIT)
- Review subject diary for IMP compliance, content and completeness; collect data from subject diary and remind subject to continue recording daily medication usage including IMP, time of meals and doses, exacerbations, rescue medication or antibiotic usage (if applicable), twice daily TNSS (AM and PM) and to bring their diary to the next visit
- Dispense IMP and administer IMP
- Schedule appointment for next visit

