6.3 Dosing and Extent of Exposure

Exposure and compliance will be summarized for the Safety Population by treatment group and overall. Comments recorded on the Compliance CRF page regarding dosing will not be applied in the computation of compliance. Exposure is the duration (days) of treatment, computed as:

Exposure= Date of Final Dose- Date of Baseline Visit + 1.

Treatment compliance will be calculated as:

Compliance (%) = 100*(Total Number of Capsules Dispensed-Total Number of Capsules Returned)/Exposure.

Summary statistics for exposure and compliance will be presented in a table with the corresponding listing for the Safety Population.

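### Compliance counts capsules documented as lost as if they were swallowed, and the SAP formula omits the four-capsules-a-day factor

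*Protocol*

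**What the plan says.** Protocol 11.6.2 takes as the compliance numerator "Total Number of Capsules Dispensed-Total Number of Capsules Returned" and divides it by four times the days of exposure. Exposure runs to the last dose: "Exposure = Date of Final Dose- Date of Baseline Visit + 1". The same section states that "Comments recorded on the Study Drug Accountability CRF page will not be applied in the computation of compliance".

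SAP 6.3 keeps the numerator and the exposure definition, and repeats the bar under another page name: "Comments recorded on the Compliance CRF page regarding dosing will not be applied in the computation of compliance". Its denominator is exposure alone, without the 4. SAP section 9, which lists departures from the protocol's methods, names only the restriction of secondary variables to the ITT Population.

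Neither document has a rule for lost or discarded capsules, an upper limit on the percentage, or a measure against the planned course. Both summarise exposure in days beside compliance.

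A second source of dosing data exists. The diary records daily study-drug use, and the Week 4 and Week 8 visits include this step: "Review subject diary for IMP compliance, content and completeness; collect data from subject diary".

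Dosing also enters the definition of the Per Protocol Population (Protocol 11.2.3, SAP 4.7), which requires "no major protocol violations, including violation of inclusion or exclusion criteria or insufficient dosing". No threshold or data source is given for the dosing part.

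**The concern.** A pill count is accurate only when whatever was not swallowed comes back. When a bottle is lost or its contents are thrown away, the correction has to come from the site's accountability record. The plan rules out using the comments on that record, so a known error stays in the figure. It always acts in one direction, towards apparent dosing.

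The missing factor 4 is a separate fault in the same formula. If the SAP were programmed as written, the whole compliance table would be four times too high, and a subject taking one capsule a day would read 100%.

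What is at stake is limited. The compliance table for the Safety Population could misstate dosing. If the same figure were used to decide who was insufficiently dosed, a subject with a small part of the course could stay in the Per Protocol analysis of SNOT-22. SAP 7.1 lists LOCF for that population as well as for ITT, so such a subject's early score could be carried to Week 8.

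**Working it through.** The documents state no numerical compliance result, so there is no figure of the plan to reproduce. The first row of the table checks that the protocol formula gives 100% for perfect dosing with full returns.

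**Inputs from the documents**
- Capsules per day: "Four (4) capsules each of IMP (oral ifetroban or matching placebo) will be taken by mouth per daily dose" (Protocol 7.3).
- Bottle size: "Quantity: 75 Capsules" (Protocol 7.3).
- Planned treatment: eight weeks = 56 days, so 56 × 4 = 224 capsules.

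**Formulas**
- Dispensed − returned = capsules taken + capsules lost, whatever number was dispensed.
- Protocol: 100 × (taken + lost) / (4 × exposure).
- SAP: 100 × (taken + lost) / exposure.
- True on-treatment adherence: 100 × taken / (4 × exposure).
- Share of planned course: 100 × taken / 224.

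| Case | Taken | Lost or not returned | Days | Protocol | SAP | True on-treatment | Planned course |
|---|---|---|---|---|---|---|---|
| A. Full dosing, leftovers returned | 224 | 0 | 56 | 224/224 = 100.0% | 224/56 = 400.0% | 100.0% | 100.0% |
| B. Full dosing, one bottle lost | 224 | 75 | 56 | 299/224 = 133.5% | 299/56 = 533.9% | 100.0% | 100.0% |
| C. 149 taken, one bottle lost | 149 | 75 | 56 | 224/224 = 100.0% | 224/56 = 400.0% | 66.5% | 66.5% |
| D. Half taken, one bottle lost | 112 | 75 | 56 | 187/224 = 83.5% | 187/56 = 333.9% | 50.0% | 50.0% |
| E. Stops Day 14, leftovers returned | 56 | 0 | 14 | 56/56 = 100.0% | 56/14 = 400.0% | 100.0% | 25.0% |
| F. Stops Day 14, nothing returned* | 56 | 94 | 14 | 150/56 = 267.9% | 150/14 = 1071.4% | 100.0% | 25.0% |

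*Case F assumes that two bottles (150 capsules) were dispensed at Week 0. The documents do not give the number, but 28 days need 28 × 4 = 112 capsules, which is more than one bottle holds. Cases A to E need no supply assumption.

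**What the cases show**
- One lost bottle adds 75/224 = 33.5 points over 56 days, and more if exposure is shorter.
- Case C is the one that misleads unnoticed: the reading looks perfect while a third of the capsules were not taken.
- The SAP column is four times the protocol column throughout. One capsule a day for 56 days gives 56/56 = 100% under the SAP.
- Case E is a correct on-treatment value. The short course shows only in the exposure days (14) or in the last column.

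**Check on a planned-course denominator.** Protocol 8.1 allows ±5 days around a visit. Perfect dosing over 51 to 61 days uses 204 to 244 capsules, which is 204/224 = 91.1% to 244/224 = 108.9% of a fixed 224. A fixed 224 would therefore mislabel some fully adherent subjects.

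**The case against.** The case against acting runs as follows. The primary analysis is ITT and never touches compliance. Leaving free-text comments out of a formula is a defensible rule set in advance, and monitors examine accountability records, including lost material (Protocol 16.3.1). A reading of 134% or 268% is impossible and so announces an accountability problem. Only a loss that happens to offset missed doses, as in case C, passes as good dosing, and the documents give no loss rate. Exposure days and early terminations are reported separately, so a Day 14 stop is visible.

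Most of this stands, and it rules out three stronger readings that a reader might infer.
- **That an early stop falsely reads as full dosing.** Dividing by days to the last dose is a recognised measure of adherence while on treatment, and exposure is summarised beside it. The limit is only that compliance alone cannot show a short course.
- **That any loss gives a full or excess reading, or that the table will always overstate dosing.** Case D reads 83.5%. Where all leftovers are returned, the protocol formula is correct for what it measures.
- **That the Per Protocol result is compromised.** Nothing ties insufficient dosing to this figure. Per Protocol membership is decided before unblinding, when exposure days, termination reasons and the diary can all be consulted.

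The objection does not rescue the bar on comments. It keeps a documented error in a reported number when the correction is already on file. Nor does it explain the missing factor 4. The SAP also differs from the supplied protocol on screening length and visit windows, so it may follow other protocol text. The two formulas disagree whatever the reason.

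**Conclusion.** The point holds in a limited form, and the plan should be corrected. As written, both documents count capsules documented as lost or discarded as taken. One 75-capsule bottle is worth 33.5 points over a 56-day course: 133.5% for a fully dosed subject, or 100% against a true 66.5%. The SAP formula also contradicts the protocol by a factor of 4, undeclared in SAP section 9, so full dosing reads 400%.

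The primary ITT analysis is unaffected. The effect is on the compliance table and, conditionally, on the Per Protocol set.

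This rests on four capsules a day for 56 days, a full bottle lost, and the loss being recorded in the barred comments. The CRF page itself is not in the documents. How often losses occur is unknown, so the size of the error in the group summaries cannot be estimated.

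**What to change.** Make these changes before unblinding.

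1. **Numerator (Protocol 11.6.2 and SAP 6.3).** Delete the sentence barring the comments. Subtract capsules documented as lost or discarded. The rule must not strike out capsules merely because they were not returned, since every swallowed capsule is unreturned. Where a bottle does not come back and its contents are unexplained, use the daily study-drug diary entries. If there is no diary either, show compliance as missing. In case C this gives 149/224 = 66.5%, and in case B 224/224 = 100%.
2. **Denominator (SAP 6.3).** Divide by 4 × exposure, as in the protocol.
3. **Second measure.** Keep on-treatment compliance and add capsules taken as a percent of the planned course. The denominator should allow for the ±5-day visit window. One way is 4 × the days to the actual Week 8 visit for a subject still on treatment then, and 224 for a subject who stopped earlier.
4. **Per Protocol rule (Protocol 11.2.3 and SAP 4.7).** State that insufficient dosing is judged on the planned-course figure, not on on-treatment compliance alone, and fix the cut-off before unblinding.

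The cost is a wording change in two documents and a little programming on data already collected. Compliance may look slightly less favourable, and the Per Protocol set may lose a few subjects.

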# 11.6.3 Efficacy Analyses

All hypothesis tests will be performed at the 0.05 level. Analyses of the primary and secondary efficacy variables will be performed using both the ITT and PP Populations. Corresponding summary statistics will be presented for all efficacy analyses.

### 11.6.3.1 Primary Analysis

The primary efficacy endpoint is the CFB in SNOT-22 score and the primary analysis is the analysis of CFB in SNOT-22 at Week 8, using Analysis of Covariance (ANCOVA), with SNOT-22 at Baseline included as the only covariate.

### 11.6.3.2 Analysis of secondary endpoints

CFB in ACQ-7 and CFB in TNSS at Week 8 will be analyzed using ANCOVA, with the corresponding value at Baseline included as the only covariate. These variables, as well as CFB in SNOT-22, at Week 4 will also be analyzed as ancillary analyses.

Analyses of CFB for other continuous efficacy variables will be performed at Weeks 4 and 8 in the same manner using ANCOVA with the corresponding value at Baseline included as the only covariate.

Any improvement in SNOT-22, ACQ-7, and TNSS (Yes or No) at Weeks 4 and 8 will be analyzed using the normal approximation to the binomial distribution, assuming unequal variances.

## 11.6.4 Safety Parameters

All safety data will be summarized. AEs will be coded using the Medical Dictionary for Regulatory Activities (MedDRA) (Version 9.0 or later). All Treatment Emergent Adverse Events (TEAEs) will be summarized by treatment group. Counts and percents will be presented by treatment group for each observed system organ class (SOC) and preferred term as defined in MedDRA.

The preferred terms and SOCs will be summarized in the following set of tables:

- All AEs;
- All AEs by maximum level of intensity;
- All AEs by closest relationship to the study medication.

The frequencies and percentages of AEs will be tabulated. Incidence, relation to study medication, and severity will be summarized.

Physical examination findings, laboratory parameters, vital signs, FEV1, weight, and corresponding changes from Baseline, as appropriate, will be summarized using descriptive statistics at each visit.

#### 12 STUDY MANAGEMENT AND DATA COLLECTION

# 12.1 Confidentiality

All information regarding the nature of the proposed investigation provided by the Sponsor or Study Monitor to the Investigator (with the exception of information required by law or regulations to be disclosed to the IRB, the subject, or the appropriate regulatory authority) must be kept in confidence by the Investigator.

The anonymity of participating subjects must be maintained. Subjects will be identified by an assigned subject number on CRFs and other study documents submitted to the Study Monitor. Documents that will not be submitted to the Study Monitor and that identify the subject (e.g., the signed informed consent document) must be maintained in strict confidence by the Investigator, except to the extent necessary to allow auditing by the appropriate regulatory authority, the Study Monitor, or Sponsor representatives.

#### 12.2 Source Documents

Source data are contained in source documents. Examples of these original documents, and data records include: hospital records, clinical and office charts, laboratory notes, memoranda, subjects' diaries or evaluation checklists, pharmacy dispensing records, recorded data from automated instruments, copies or transcriptions certified after verification as being accurate and complete, microfiches, photographic negatives, microfilm or magnetic media, x-rays, subject files, and records kept at the pharmacy, at the laboratories, and at medico-technical departments involved in the clinical trial.

# 12.3 Case Report Forms

It is the responsibility of the Investigator to maintain adequate and accurate eCRFs designed by the Sponsor to record (according to Sponsor instructions) all observations and other data pertinent to the clinical investigation in a timely manner. All CRFs should be completed in their entirety in a neat, legible manner to ensure accurate interpretation of data.

Should a correction be made, the corrected information will be entered in the e-CRF overwriting the initial information. An audit trail allows for identifying the modification.

Data are available within the system to the Sponsor as soon as they are entered in the e-CRF.

The computerized handling of the data by the Sponsor when available in the eCRF may generate additional requests to which the Investigator is obliged to respond by confirming or modifying the data questioned. The requests with their responses will be managed through the eCRF.

#### 12.4 Records Retention

According to CFR21 312.62 (c) and ICH E6 4.9.5, all CRFs, as well as supporting documentation and administrative records, must be retained by the Investigator for a minimum of two years following notification that the appropriate regulatory authority has approved the product for the indication under study, if no application is to be filed or if the application is not approved for such indication, until two years after the investigation is discontinued and FDA is notified. It is the sponsor's responsibility to inform the investigator as to when these documents no longer need to be retained. No study documents will be destroyed or moved to a new location without prior written approval from the Sponsor. If the Investigator relocates, retires, or withdraws from the clinical study for any reason, all records required to be maintained for the study should be transferred to an agreed upon designee, such as the Study Monitor, another Investigator, or the institution where the study was conducted.

## 13 STUDY MONITORING, AUDITING, AND INSPECTING

### 13.1 Study Monitoring Plan

The progress of the study will be monitored by using the following methods:

- Periodic on-site visit(s)
- Telephone communications, as needed, among the Investigator, Clinical Monitor and Medical Monitor
- Review of CRFs and clinical records

### 14 ETHICAL CONSIDERATIONS

This study will be conducted according to the standards of FDA, ICH, GCP Guidelines, IRB regulations, any applicable government regulations and procedures. This protocol and any amendments will be submitted to a properly constituted IRB for approval of the study conduct.

#### 14.1 Informed Consent

Written informed consent must be obtained from each subject (or the subject's legal guardian/representative) before performing any Screening Period evaluations. The signed informed consent document will be retained by the Investigator, and a copy will be given to the subject or subject's legal guardian/representative. The informed consent document, which is prepared by the Investigator, must have been reviewed and approved by the Sponsor and the Investigator's IRB before the initiation of the study. The document must contain the 20 elements

of informed consent described in ICH E6 4.8 (Appendix 16.1). Appendix 16.1 provides further details regarding the specific requirements for informed consent. In addition, subjects of appropriate intellectual maturity should provide written informed assent, as determined by the institution's IRB or local legal requirement.

### 14.2 Protocol Compliance

Substantive changes in the protocol include changes that affect the safety of subjects or changes that alter the scope of the investigation, the scientific quality of the study, the experimental design, dosages, assessment variable(s), the number of subjects treated, or the subject selection criteria. Such changes must be prepared as a protocol amendment by the Study Monitor and implemented only upon joint approval of the Sponsor, Investigator, and the Study Monitor. A protocol amendment must receive IRB approval before implementation. In parallel with the IRB approval process, the protocol amendment will be submitted to the appropriate regulatory authority as an amendment to the regulatory submission under which the study is being conducted. If a protocol amendment requires changes in the informed consent document, the revised informed consent document prepared by the Investigator must be approved by the Sponsor, Study Monitor, and the IRB.

Emergency departures from the protocol that eliminate an apparent immediate hazard to a particular subject and that are deemed crucial for the safety and well-being of that subject may be instituted for that subject only. The Investigator or other attending physician also will contact the Medical Monitor as soon as possible in the case of such a departure. These departures do not require pre-approval by the IRB; however, the IRB and Medical Monitor must be notified in writing as soon as possible after the departure has been made. In addition, the Investigator will document in the subject's CRF the reasons for the protocol deviation and the ensuing events.

